This clinical feasibility study will investigate the use of PSMA-PET/MRI to guide radiation treatment planning and delivery in patients with known or suspected locally metastatic prostate cancer at the time of diagnosis. The patients will undergo a single PSMA-PET/MRI (or PET/CT in some circumstances) prior to initiation of treatment. Following development of a PSMA-PET guided radiation treatment plan, therapeutic radiation will be delivered per standard-of-care parameters and assessments of feasibility and tolerability will be performed. A total of 10 patients will be enrolled in this study. If the PET/MRI demonstrates a suspicious finding that may make a patient ineligible for radiation therapy, the treating clinician (including urology and radiation oncology) will be alerted, and the decision to pursue biopsy and/or alter the patient's treatment plan will be based on standard of care imaging and consensus after presenting the case at the GU tumor board.

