6.2 Study Objectives

Specific Aim #1: Determine the concordance of imaging findings for PSMA-PET/MRI and MRI of the pelvis and prostate gland.

Hypothesis #1: PSMA-PET/MRI will identify more regional lymph node metastases than MRI alone.

There have been numerous prior studies demonstrating the value of MRI for the locoregional staging for PCa. We expect the simultaneous acquisition of MRI and PSMA PET data to provide valuable preoperative staging information, with PSMA PET detecting metastatic disease in subcentimeter pelvic lymph nodes not identified with MRI alone. Additionally, PSMA-PET/MRI provides whole body staging in regions not evaluated by pelvic MRI and may detect additional distant metastases.

Specific Aim #2: Establish feasibility and assess acute toxicity of PSMA-PET/MRI directed pelvic radiotherapy.

Hypothesis #2: PSMA-PET/MRI directed radiation therapy will be feasible in the vast majority of patients (>90%) and can be safely administered without increased acute radiation toxicities.

The primary goal of Specific Aim 2 is to provide preliminary information to confirm the feasibility of radiation dose escalation to the suspicious LNs identified on PSMA-PET/MRI. If results from this trial are supportive, this will lead to a larger clinical trial evaluating efficacy and disease outcomes between patients who have undergone PSMA-PET/MRI directed radiotherapy versus standard-of-care pelvic radiotherapy.

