6.5.2 RADIOTHERAPY TARGET VOLUME DELINEATION (Figure 1)

Varian Eclipse software (Varian Medical Systems LLC, Palo Alto, CA, USA) will be used for radiotherapy target delineation and treatment planning. For all patients we will initially define traditional standard-of-care clinical target volumes for the treatment of high risk prostate cancer:

CTV_{P+SV} will contain the entire prostate gland and portion of the seminal vesicles at risk for tumor involvement. At least the proximal 1cm of the seminal vesicles. In cases where gross seminal vesicle invasion is identified the entire seminal vesicles will be included.

CTV_{eLN} will contain the elective lymph node target volumes. Elective nodal regions will be delineated in accordance with published consensus guidelines⁷ and will include the obturator, internal iliac, external iliac, and distal common iliac chains.

Next, the PSMA PET scan will be rigidly co-registered to radiation simulation CT scan. Rigid co-registration is preferred for two specific reasons: (1) we recognize that 8-10 weeks of androgen suppression between PSMA-PET/MRI and radiotherapy simulation may lead to changes in LN size that may lead to error in deformable registration, and (2) prior experience with PSMA-PET/MRI co-

[figure not shown]

Figure 1: Example of fluciclovine-PET/MRI directed radiotherapy treatment planning. Left image shows the $[^{18}\text{F}]$ fluciclovine PET-MRI with lower window of PET window set to 1.3 times blood pool. The suspicious LN is segmented in red. Right image is the treatment planning CT for the same patient with $\text{CTV}_{\text{LN BOOST}}$ delineated in green and the associated PTV in blue.

registration in the biochemical recurrence setting indicates that rigid co-registration results in good anatomic agreement in the majority of cases⁸. Using the registered PSMA-PET/MRI we will delineate an additional CTV:

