6.5.5 Study Variables and Key Endpoints

For specific aim 1, we will assess the concordance between prostate MRI and PSMA-PET/MRI for the detection of seminal vesicle invasion and pelvic metastatic disease. The total number of pelvic nodal metastases detected on MRI and PSMA-PET/MRI will be compared. The confidence in detection of seminal vesicle invasion on a 0-3 Likert scale will also be compared between MRI and PSMA-PET/MRI. The primary endpoint for specific aim 1 number of patients who demonstrate pelvic LN metastases on PSMA-PET/MRI that were not detected on conventional anatomic imaging. We expect at least 25% of patients to demonstrate pelvic LN metastases that were not detected on conventional anatomic imaging.

For specific aim 2, study participants who remain eligible for pelvic radiation therapy (e.g. no distant metastases) will be subdivided into two cohorts: those without suspicious extraprostatic activity on PSMA-PET/MRI and those whose PSMA-PET/MRI demonstrates suspected seminal vesicle invasion and/or pelvic nodal metastatic disease. Those without suspicious extraprostatic uptake will undergo standard-of-care radiation therapy. Patients with positive PSMA-PET/MRI scans will undergo radiation treatment planning with a boost given to the suspicious lesions. The primary endpoint of specific aim 2 is to assess the number of patients with positive PSMA-PET/MRI scans where the radiation boost is feasible. We expect that the radiation treatment planning will be feasible in at least 90% of patients with positive PSMA-PET/MRI scans. A secondary endpoint is to compare the frequency of acute radiation toxicities between the cohorts. We expect that less than 15% of patients who undergo PSMA-PET/MRI directed LN radiotherapy boost will experience CTCAE v5.0 grade 3+ genitourinary or gastrointestinal toxicities and that no patient will experience a grade 5 genitourinary or gastrointestinal toxicity. All grade 3 toxicities will be reviewed by the radiation oncology sub-investigator. If any grade 4 or 5 events occur, the cases will be reviewed among members of the study team and the study will potentially be paused/terminated if there is concern that deviation from standard of care radiation therapy has caused undue harm to the patient.

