6.6 Statistical Considerations

6.6.1 Study Design and Sample Size Calculation

Given the pilot nature of this study and small sample size, no formal power or sample size calculations were performed.

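### Acute toxicity is compared by scan result rather than by nodal boost received, and with ten patients a lack of difference cannot support Hypothesis 2

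*Combined protocol and SAP*

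**What the plan says.** Hypothesis 2 (Section 6.2) is that PET-directed radiotherapy "can be safely administered without increased acute radiation toxicities". Section 6.0 likewise ties the toxicity evaluation to the extra radiation given to suspicious pelvic nodes.

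Section 6.5.5 divides men still eligible for pelvic radiotherapy into two cohorts by scan result. One has no suspicious extraprostatic activity; the other is "those whose PSMA-PET/MRI demonstrates suspected seminal vesicle invasion and/or pelvic nodal metastatic disease". On treatment it says: "Those without suspicious extraprostatic uptake will undergo standard-of-care radiation therapy". Scan-positive men are to be planned with their suspicious lesions boosted. The comparison follows: "A secondary endpoint is to compare the frequency of acute radiation toxicities between the cohorts". The next sentence expects grade 3+ genitourinary or gastrointestinal toxicity in under 15%, but among men who undergo the nodal boost.

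In Section 6.5.2, standard volumes come first ("For all patients we will initially define traditional standard-of-care clinical target volumes"), and SVI is handled there: "In cases where gross seminal vesicle invasion is identified the entire seminal vesicles will be included". One further PET-directed volume is then defined, and it contains lymph nodes only. Section 6.5.3 prescribes three dose levels (prostate plus seminal vesicles, nodal boost, elective nodes) and none specific to SVI.

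On size, Section 6.0 says "A total of 10 patients will be enrolled in this study" and Section 6.6.1 says "no formal power or sample size calculations were performed". Section 6.6.3 makes the safety analysis descriptive, with frequencies and percentages. Exact intervals are specified there for Aim 1 only.

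**The concern.** A claim about the effect of added radiation needs groups defined by whether that radiation was given. Scan result is only a proxy, and here it departs from exposure in at least one way and possibly two. The paragraph also uses two different toxicity groups without saying so, so the between-cohort table and the 15% expectation could be reported on different men.

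Scan result is itself a measure of disease extent. Even if every scan-positive man were boosted, a difference, or its absence, could reflect extent of disease or treated volume rather than the boost. No adjustment is planned, and none is workable at this size.

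What is at stake is the reading of the result. Section 6.2 says supportive results will lead to a larger trial. A table with few events in both cohorts could be taken as confirming that toxicity is not increased, which these data cannot show.

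**Working it through.** The plan gives no power, margin or reference-rate figure to reproduce. The check therefore has two parts: who falls in each group, and what ten men can show.

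**1. Group membership, from Sections 6.5.2, 6.5.3 and 6.5.5**

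| Patient | Cohort compared | Nodal boost | In the 15% group |
|---|---|---|---|
| No suspicious extraprostatic activity | Negative | No | No |
| Positive nodes, boost delivered | Positive | Yes | Yes |
| Positive nodes, boost infeasible | Positive | No | No |
| SVI only | Positive | None defined in 6.5.2–6.5.3; 6.5.5 implies some boost | No, as it counts nodal boosts |

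The positive cohort and the 15% group coincide only if the last two rows are empty.

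**2. Could the infeasible row be filled?** Section 6.5.5 expects feasibility in at least 90% of scan-positive men. Assume exactly 90%, independent between men. The chance that at least one of k is not boosted is 1 − 0.9^k:
- k = 3: 27%
- k = 5: 41%
- k = 7: 52%

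**3. Effect of mixing (illustrative).** Let s be the share of the positive cohort without a nodal boost, and suppose those men carry the reference rate p0. The apparent excess is then (1 − s)(p_boost − p0). With assumed rates of 15% and 5%:
- s = 20%: 0.8 × 10 = 8 points
- s = 40%: 0.6 × 10 = 6 points

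The documents give no value for s, and it could be zero.

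**4. Precision of the contrast.** The split is not given, so 3/7, 5/5 and 7/3 are assumed. With no events in either group, the 95% Newcombe limits are minus the Wilson upper limit of the negative cohort and plus that of the positive cohort. The Wilson upper limit for 0/n is z²/(n + z²), with z² = 3.84.
- n = 5: 3.84/8.84 = 0.434
- n = 3: 3.84/6.84 = 0.561
- n = 7: 3.84/10.84 = 0.354

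The intervals for positive minus negative are:
- 5 v 5: −43 to +43 points
- 3 positive v 7 negative: −35 to +56 points
- 7 positive v 3 negative: −56 to +35 points

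**5. Precision in boosted men alone.** With zero events, the two-sided 95% exact upper limit is 1 − 0.025^(1/n):
- n = 3: 70.8%
- n = 5: 52.2%
- n = 7: 41.0%
- n = 10: 30.8%

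The limit first falls below 15% at n = 23 (14.8%), which is more than the whole study. If the true rate were 30%, twice the benchmark, five boosted men would still show no event with probability 0.7^5 = 17%.

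**The case against.** The strongest reply is that the plan already discloses its limits. It is a pilot with no power calculation, toxicity is a secondary endpoint, the analysis is descriptive and no test is proposed. The between-cohort contrast is also not the only safeguard: the 15% benchmark is set in boosted men, every grade 3 event is reviewed, and grade 4 or 5 events may pause or end the study. Confounding by disease extent is inherent in a ten-patient non-randomised study, and regrouping does not remove it.

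Much of this stands. It rules out criticising the plan for lacking power or a test. It does not rescue the grouping, because a descriptive table still needs rows that match the question. The 15% benchmark is absolute and supplies no reference rate for an increase.

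A reader might infer that SVI-only men definitely sit unboosted in the boosted cohort. The documents do not settle that. Section 6.5.5 read literally boosts every suspicious lesion, SVI included, while Sections 6.5.2–6.5.3 define only a nodal boost. SVI may also enlarge the prostate and seminal vesicle volume, so these men are not shown to be treated like scan-negative men either. Pooling them with that group could create a new mixture.

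**Conclusion.** The point holds at the level of grouping and wording. The toxicity comparison is by scan result, it differs from the boosted denominator used in the same paragraph, and it does not isolate the added radiation. At ten men or fewer, an observed absence of difference is compatible with differences of roughly 43 points either way at 5 v 5, and 0/5 boosted is compatible with a rate up to 52%. It therefore cannot support the no-increase part of Hypothesis 2.

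The sizes rest on assumed splits and zero events. The number of non-boosted scan-positive men is unknown, so the dilution figures are illustrative only. Regrouping by treatment received removes the mixing. It does not remove confounding by disease extent or the imprecision, so the disclaimer is needed as well.

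**What to change.** 1. In Sections 6.5.5 and 6.6.3, report acute toxicity by whether the nodal boost was planned and delivered, using the same denominator as the 15% expectation.
2. List SVI-only men, and scan-positive men who were not boosted, on separate lines. Do not pool them with scan-negative men.
3. Reconcile Section 6.5.5 with Sections 6.5.2–6.5.3 on whether suspected SVI receives a boost. This is for the investigators to settle; the analysis only needs one consistent definition.
4. Give exact 95% intervals for each toxicity proportion, as is already done for Aim 1.
5. State that the between-group contrast is descriptive and not evidence of the boost's effect. Soften Hypothesis 2 to describing acute toxicity in boosted men.

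The cost is protocol wording, very small subgroups in the table and a less favourable-sounding safety claim. No patient procedure or extra data collection is added. A no-boost comparison plan for each boosted man could be informative about dose, but it would not measure toxicity and is not required here.

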6.5.6 Study Termination

The study will stop enrolling patients once the target number has been reached.

6.6 Statistical Considerations

6.6.1 Study Design and Sample Size Calculation

Given the pilot nature of this study and small sample size, no formal power or sample size calculations were performed.

6.6.2 Definition of Analyzed Study Population

Study population is adult males with treatment-naïve prostate adenocarcinoma who meet the inclusion criteria listed above.

6.6.3 Analysis

Demographic and clinical characteristics of all the enrolled patients will be summarized using descriptive and graphical statistics. Mean and standard deviation will be provided for continuous variable and counts and percentage will be for categorical variables. To ensure the quality of imaging data, imaging data from three readers will be assessed first using Kappa statistics (K) for inter-rater agreement.

For the primary analysis in Aim 1, the number of patients who are identified with lymph node metastases (positive nodal) will be counted, and percentage and 95% exact confidence interval will be calculated using the Clopper-Pearson method for PSMA-PET/MRI and MRI respectively.

Concordance and agreement between two methods will be evaluated using Cohen's kappa statistic, κ . For the primary analysis in Aim 2, SUV thresholding, CTV, and other imaging parameters between PSMA-PET/MRI and MRI will be determined using the Bland-Altman plot analysis in addition to descriptive analysis. Safety analysis of acute radiation toxicities related AE/SAE in Aim 2 will be descriptive, such as frequency and percentage will be reported. We will also report the frequency of patients with any grade 3 GI or GU toxicity, and any grade 4-5 toxicity. All statistical analysis will be carried out using the Statistical Analysis Software SAS v 9.4.

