6.3 Investigational Plan

6.3.1 Study Design

- Prospective IRB-approved study enrolling 10 patients with locally metastatic prostate cancer for pretreatment PSMA-PET/MRI prior to the initiation of treatment
- All patients will undergo standard-of-care clinical evaluation and imaging workup with nuclear medicine bone scan and either CT of the abdomen and pelvis or MRI pelvis
- Patients will undergo standard-of-care androgen deprivation therapy following PSMA-PET/MRI and prior to radiation therapy
- If study PET/MRI demonstrates a suspicious finding that may preclude a patient radiation therapy, the treatment team will be alerted to potentially investigate the finding further (i.e. additional imaging or biopsy)
- Acute radiation toxicities will be assessed at standard-of-care intervals

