6.4.6.3 PET/MRI Imaging Interpretation and Storage

Images from the PET/MRI will be stored and reviewed using a commercially available software package (MIM Encore, Cleveland, OH) and not be available for viewing in the institutional PACS or patient's medical record. This is in an effort to blind the treating physicians from making clinical decisions on an experimental imaging technique. The prostate MRI images will be sent to clinical PACS and the medical record as part of standard-of-care imaging and can be used in the clinical-decision making process. No formal interpretation will be generated for the $[^{68}\text{Ga}]$ PSMA-PET portion of the PET/MRI study, but the prostate MRI will have a clinical interpretation by a dedicated abdominal radiologist who will also be blinded to the patient enrollment in the study. Dedicated study readers from both abdominal imaging and molecular imaging will interpret first the prostate MRI alone, and then the fused PET/MRI to assess potential added value from the PET/MRI. The study readers will be blinded to the results of any additional standard-of-care

imaging and clinical evaluation and will only have knowledge that the patient has biopsy-proven prostate cancer.

Assessment of the prostate MR primary lesion location, extracapsular extension (ECE), seminal vesicle invasion (SVI), and metastatic disease will be evaluated utilizing a Likert scale from 1-5 to indicate reader confidence utilizing PI-RADS v2.0 criteria. The PSMA-PET/MRI will be evaluated with the same 1-5 Likert scale utilizing the PSMA-RADS v1.0 criteria.[16] The number of pelvic nodal metastases detected at each lymph node station will be recorded. Exams will be interpreted by three radiologists/nuclear medicine physicians to evaluate interreader agreement with disputes resolved by consensus.

MRI Data Analysis: The MRI images will be qualitatively analyzed.

Qualitative analysis: A visual evaluation of the pelvic lymph nodes with suspected metastatic disease will be performed. The number of positive metastatic lymph nodes and their nodal stations will be recorded. Nodal stations that will be examined include right and left common iliac, internal iliac, external iliac, obturator, inguinal, and retroperitoneal (total of 11 stations per patients).

MRI Images

- 1 = Normal lymph nodes
- 2 = Mild prominence not meeting RECIST criteria for adenopathy (low suspicion)
- 3 = Borderline enlarged by RECIST criteria (intermediate suspicion)

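### The Aim 1 primary analysis in 6.6.3 neither estimates the Aim 1 primary endpoint defined in 6.5.5 nor gives it a confidence interval

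*Combined protocol and SAP*

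**What the plan says.** Section 6.5.5 of the combined protocol and SAP gives the Aim 1 primary endpoint as the "number of patients who demonstrate pelvic LN metastases on PSMA-PET/MRI that were not detected on conventional anatomic imaging". It adds: "We expect at least 25% of patients to demonstrate pelvic LN metastases that were not detected on conventional anatomic imaging".

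Section 6.6.3 describes the Aim 1 primary analysis differently. There, "the number of patients who are identified with lymph node metastases (positive nodal) will be counted", and a percentage and "95% exact confidence interval will be calculated using the Clopper-Pearson method for PSMA-PET/MRI and MRI respectively". It continues: "Concordance and agreement between two methods will be evaluated using" Cohen's kappa. It does not say whether kappa is computed per patient, per nodal station or per node.

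The comparator also varies. Hypothesis 1 in 6.2 reads "PSMA-PET/MRI will identify more regional lymph node metastases than MRI alone", and 6.6.3 likewise uses MRI. The endpoint in 6.5.5 uses conventional anatomic imaging, and 6.3.1 has every patient worked up with "nuclear medicine bone scan and either CT of the abdomen and pelvis or MRI pelvis", so that imaging may be CT. Under 6.4.6.3 the study readers "will interpret first the prostate MRI alone, and then the fused PET/MRI to assess potential added value from the PET/MRI", and they are blinded to standard-of-care imaging.

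Both reads use 1-5 scales. Section 6.4.6.3 names no score at which a node counts as positive; an intermediate score is used only to select nodes for quantitative measurement.

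**The concern.** The endpoint is a paired quantity: for each patient, did PSMA-PET/MRI show a node that the comparator did not? Two separate percentages describe how often each modality is positive. They do not say how often one finds disease that the other misses. Kappa summarises agreement and is not an estimate of that proportion either.

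The count itself would probably be reported, because the endpoint is a number of patients. But 6.6.3 attaches no interval and no counting rule to it. The comparator, the positivity cut and the treatment of patients positive on both scans could therefore be settled after the reads are known. Section 6.0 says larger studies will be designed from these results, so the estimate carries forward.

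**Working it through.** The plan has no figure to reproduce: 6.6.1 states that no power or sample size calculation was done. The check asks what the planned outputs would tell us about the endpoint.

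**Inputs.** n = 10 (6.0, 6.3.1) and the 25% expectation (6.5.5). The positive counts and kappa values below are assumed for illustration, as are complete reads on all 10 patients and a patient-level kappa.

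**Notation.** Let p and m be the numbers positive on PSMA-PET/MRI and on the study MRI, a the number positive on both, and b the number PSMA-positive and MRI-negative. Then a = p − b, and the MRI-positive, PSMA-negative count is m − p + b.

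**Step 1: do the planned outputs fix b?** Chance agreement is pe = [pm + (n − p)(n − m)]/n². Solving kappa for b gives

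b = [n(1 − pe)(1 − kappa) + p − m]/2.

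For given margins, b is therefore unique. Kappa is undefined only when both margins are 0/10 or both are 10/10, and then b = 0. The two percentages alone do not suffice: with p = 6 and m = 5, b can be 1, 2, 3, 4 or 5 (kappa 0.8, 0.4, 0, −0.4, −0.8).

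**Step 2: Example A, p = 6, m = 5, kappa = 0.80.** pe = (30 + 20)/100 = 0.5, so b = [10 × 0.5 × 0.2 + 1]/2 = 1 and a = 5. Clopper-Pearson limits are the 2.5% quantile of Beta(x, n − x + 1) and the 97.5% quantile of Beta(x + 1, n − x).

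| Reading of the 6.5.5 endpoint | Possible value | Exact 95% CI |
|---|---|---|
| Patient level, study MRI as comparator | b = 1/10 | 0.3% to 44.5% |
| Node level, study MRI as comparator | b to a + b = 1/10 to 6/10 | 0.3% to 44.5% at 1/10; 26.2% to 87.8% at 6/10 |
| Standard-of-care CT or MRI as comparator | 0 to a + b = 0/10 to 6/10 | 0% to 30.8% at 0/10; 26.2% to 87.8% at 6/10 |

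On the node-level reading, b is only a lower bound, because a patient positive on both scans with an additional PSMA-only node also qualifies. With standard-of-care imaging as comparator, b need not bound the endpoint at all, since that imaging may show a node the study MRI missed.

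**Step 3: Example B, p = m = 8, kappa = 1.0.** pe = (64 + 4)/100 = 0.68, so b = [10 × 0.32 × 0 + 0]/2 = 0 and a = 8. The node-level endpoint, with the study MRI as comparator, can be anything from 0/10 (0% to 30.8%) to 8/10 (44.4% to 97.5%).

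**Step 4: the 25% mark.** 0.25 × 10 = 2.5, so 3/10 is the smallest count that reaches it (6.7% to 65.2%). Example A spans it on the second and third readings.

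**The case against.** The strongest reply is that little hangs on this. The study is a 10-patient pilot, the 25% is an expectation without a decision rule, and once x/10 is reported anyone can attach the exact interval, by a method 6.6.3 already names. This stands as a limit on the consequence. It does not answer the undefined x. The pilot setting excuses the absence of a power calculation, not the absence of an estimate of the plan's own primary endpoint.

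A second reply is that b can be back-calculated. That is true if kappa is per patient and the study MRI is the comparator. Even then b equals the endpoint only on the patient-level reading, and no interval is planned for it.

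A third is that the ranges ignore other planned data. Section 6.4.6.3 records node counts by station, and 6.5.5 compares total node counts. With the study MRI as comparator, a station with more PSMA nodes than MRI nodes proves that a PSMA-only node exists, so these data would often narrow the range. They do not close it, because equal counts in a station can be different nodes. Reaching 8/10 in Example B with equal station counts in all eight patients is possible but extreme.

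A fourth is that the comparator could properly be conventional imaging. Sections 6.0 and 6.1 speak of nodes missed by CT and/or MRI, and that choice would ease the PET/CT problem. This is fair: the essential request is for one named comparator. Finally, 6.5.2 does give a numeric uptake criterion for nodes entering the boost volume, but nothing links it to positivity for Aim 1.

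**Conclusion.** The concern holds. The stated primary analysis addresses a different quantity from the stated primary endpoint, and no other section supplies the missing estimate. The mismatch follows from the text and needs no assumption. The numerical ranges rest on assumed margins, complete reads in 10 patients and a patient-level kappa. They show what the outputs listed in 6.6.3 leave open, not how likely each value is. This should be fixed, but it does not undermine the study: the consequence is confined to how the main Aim 1 estimate is defined and how its uncertainty is reported.

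**What to change.** In 6.6.3, make the Aim 1 primary analysis the number and proportion of patients with at least one pelvic node positive on the consensus PSMA-PET/MRI read and not positive on the comparator read, with a Clopper-Pearson 95% interval. In support of that:

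- Name one comparator in both 6.5.5 and 6.6.3. The study MRI read fits Hypothesis 1 and the MRI-then-fused reading order.
- Fix the positivity cut on each 1-5 scale before any reads.
- Match nodes individually between reads, not by differences in station counts. If MRI calls one node and PSMA another in the same station, the difference is 1 − 1 = 0, yet the patient qualifies. The node-level work already planned in 6.4.6.3 for nodes of at least intermediate suspicion can carry the match.
- State how patients imaged with PET/CT under 6.4.6.2, who have no study MRI, enter the denominator.
- Keep the per-modality percentages and a patient-level kappa, with its 2×2 table, as secondary.

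With the study MRI as comparator there is no new scan or read, only a match field for each positive node. Matching nodes against standard-of-care CT or MRI would need an extra node-level read, because the study readers are blinded to that imaging; a patient-level comparison could use the clinical result after the blinded reads.

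The estimate remains descriptive and wide. The number of PET/CT patients is not given. If 0, 1 or 2 are left out, three events give 3/10 (6.7% to 65.2%), 3/9 (7.5% to 70.1%) or 3/8 (8.5% to 75.5%).
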